6.3 Measures to Minimize Bias: Randomization

This is an open-label study and all eligible participants will receive AZD7442.

For the PK sample collected post Day 1 during the first 14 days, participants will be randomized to have a blood sample collected on either Day 4, Day 8, Day 11, or Day 15 (1:1:1:1) using the IRT.

The Investigator(s) will:

- 1 Obtain signed informed consent or assent from the potential participant, or their guardian/legal representative, before any study specific procedures are performed.
- 2 Determine participant eligibility.
- 3 Assign the eligible participant unique SID via the IRT.
- 4 Participants will be allocated to receive AZD7442 administered IM or IV
- 5 Participants will be assigned the Day of PK sampling (Day 4, Day 8, Day 11, or Day 15)

If a participant withdraws from the study, then his/her enrollment/SID cannot be reused. Withdrawn participants will not be replaced.

6.4 Study Intervention Compliance

When the individual dose for a participant is prepared from a bulk supply, the preparation of the dose will be confirmed by a second member of the study site staff.

Dosing will take place under the guidance of study personnel, and may occur at study sites, mobile units, or other health care facilities. The date, and time if applicable, of dose administered will be recorded in the source documents and recorded in the eCRF. The dose of study intervention and study participant identification will be confirmed at the time of dosing by a member of the study site staff other than the person administering the study intervention. If a problem occurs during dosing, such as needle break, no re-dosing is permitted.

6.5 Concomitant Therapy

Any medication or vaccine (including over-the-counter or prescription medicines, vitamins, and/or herbal supplements) that the participant is receiving at the time of enrollment or receives during the study must be recorded along with:

- Reason for use
- Dates of administration including start and end dates
- Dosage information including dose and frequency

The Study Physician should be contacted if there are any questions regarding concomitant or prior therapy.

Permitted, prohibited, and restricted medications are summarized in [Table 11](#). Restricted drugs of abuse and alcohol are summarized in [Table 12](#).

Table 11 Summary of Permitted, Prohibited, or Restricted Medications

Use category	Type of medication/treatment	Timeline/instructions
Permitted	Routine vaccines ^a	Licensed influenza vaccines are permitted at any time. All other routine vaccines are permitted beginning > 30 days after IMP dose COVID-19 vaccines are permitted before (> 14 days before study entry) and during the study, > 14 days after IMP administration study Day 1. For guidance during the study, see Section 6.5.1).
	Allergen immunotherapy	Allowed if participant has been receiving stable desensitization therapy for allergies for at least 30 days prior to Day 1 and there is no anticipated change during the treatment period. Allergen immunotherapy should not be administered on the same day as IMP. Non-prescription treatments for allergies such as antihistamines, decongestants, and nasal steroids are permitted.
	Commercial biologics (except for COVID-19 prophylaxis or treatment), prednisone, immunosuppressive medications (eg, azathioprine, tacrolimus, cyclosporine, methotrexate, hydroxychloroquine, or cytotoxic chemotherapy)	Allowed, provided the participant is stable on maintenance dose (at steady state) prior to Day 1 and up to Day 29, OR Allowed if participant is hospitalized for treatment of COVID-19 Biologics (eg, palivizumab) should not be administered on the same day as IMP
	Participants may take concomitant medications prescribed by their primary care provider for management of chronic medical conditions and/or for health maintenance. Primary care providers, or where appropriate Investigators, should prescribe appropriate concomitant medications or treatments deemed necessary to provide full supportive care and comfort during the study.	

Table 11 Summary of Permitted, Prohibited, or Restricted Medications

Use category	Type of medication/treatment	Timeline/instructions
Prohibited	Products indicated for the treatment or prevention of SARS-CoV-2 or COVID-19 (including those under investigation or authorized under early access provisions) Convalescent COVID-19 plasma and sera	Note: For participants who become hospitalized with COVID-19, receipt of approved/licensed treatment options are permitted, and they should be treated according to local standard of care, including investigational agents under Emergency Use Authorization or equivalent regulations.
	Hydroxychloroquine	Use of hydroxychloroquine is acceptable if used chronically for autoimmune disease, and the dose is stable prior to Day 1 and up to Day 29.
	Chloroquine	Use of chloroquine is acceptable if used to treat a parasitic infection.
	Ivermectin	Use of ivermectin is acceptable if used to treat a parasitic infection.
	HIV protease inhibitors	HIV protease inhibitors are acceptable if used chronically for HIV infection, and the dose is stable prior to Day 1 and up to Day 29.
	Hyperimmune globulin and immune globulin products	Previous use of hyperimmune globulin/ immune globulin is allowed if there is an adequate washout period prior to study start \geq 5 half-lives of the drug with no plan to dose during the study period.
Restricted	Contraceptive methods	See Section 5.1

^a The potential impact of AZD7442 on COVID-19 vaccines is not known and has not been studied. See Section 6.5.1 for instructions on COVID-19 vaccinations.

COVID-19, coronavirus disease 2019; HIV, Human immunodeficiency virus; IMP, Investigational medicinal product; SARS-CoV-2, severe acute respiratory syndrome coronavirus 2.

Table 12 Summary of Restricted Drugs of Abuse and Alcohol

Amphetamine	Benzodiazepines
Ethanol	Methadone Metabolites
Cannabinoids	Barbiturates
Cocaine	Phencyclidine
Opiates	Methamphetamines
Tricyclic anti-depressants (TCA)	

6.5.1 Receipt of COVID-19 Vaccines During the Study

Individual participants are encouraged to receive a COVID-19 vaccination when they become eligible and it is locally available. If a participant plans to receive a COVID-19 vaccine within 14 days of study Day 1 (AZD7442 administration) they should delay starting in the study until > 14 days after their last dose of vaccine (Section [5.2](#)). Available data suggests that AZD7442 may provide 6 months of protection against pre-Omicron SARS-CoV-2 variants but due to a reduced in vitro neutralization against the Omicron variant, AZD7442 may provide a different duration of protection against Omicron. Protection has not yet been demonstrated in children.

Theoretically, in the presence of adequate neutralizing antibody titers, expected for the durations noted, an appropriate and effective response to the vaccine could be impaired. Data from animal studies reported that prior AZD7442 administration did not alter either the cellular or the humoral immune responses elicited by subsequent COVID-19 vaccinations. Based on these results, AZD7442 is not anticipated to interfere with vaccine efficacy. If the participant decides to receive the vaccination the participant can proceed and continue in the study. If a participant has a breakthrough case of COVID-19 during the study despite being previously vaccinated, they should be managed using standard of care.

For participants who have received IMP and develop symptomatic COVID-19 at some point in the study:

- There is no reason to believe that administration of a vaccine during acute COVID-19 illness will ameliorate the illness.
- In most mAb recipients, an infection-induced immune response will occur, and this response should be protective.
- The risk associated with receiving a vaccine after resolution of the illness should be low.

6.6 Dose Modification

The DSMB may recommend modifications to the doses outlined in [Table 6](#) based on available safety and tolerability data. See Appendix [A 5](#).

6.7 Intervention After the End of the Study

No intervention will be provided at the end of this study.

7 DISCONTINUATION OF STUDY INTERVENTION AND PARTICIPANT DISCONTINUATION/WITHDRAWAL

7.1 Discontinuation of Study Intervention

Participants will receive a single IM dose of AZD7442 (administered as a single IM injection containing AZD8895 followed by a single IM injection containing AZD1061) or a single IV

dose of AZD7442 (administered by co-infusion of AZD8895 and AZD1061 in the same bag).

It may be necessary for a participant to temporarily interrupt their injection/infusion of IMP. If the injection of IMP is not resumed (ie, it is discontinued), the participant should remain in the study to be evaluated.

Note that discontinuation of IMP is NOT the same thing as withdrawal from the study.

7.2 Participant Withdrawal from the Study

- A participant may withdraw from the study at any time at his/her own request, the request of their parent or legal guardian, or at the discretion of the Investigator for safety, behavioral, compliance, or administrative reasons. This is expected to be uncommon.
- A participant who considers withdrawing from the study must be informed by the Investigator about modified follow-up options (eg, telephone contact, a contact with a relative or treating physician, or information from medical records).
- At the time a participant withdraws consent or is withdrawn from the study, if possible, an Early Discontinuation visit should be conducted, as shown in the SoA ([Table 3](#)). See the SoA for data to be collected at the time a participant withdraws consent or is withdrawn from the study and follow-up and for any further evaluations that need to be completed.
- If the participant withdraws consent for disclosure of future information, the Sponsor may retain and continue to use any data collected before consent was withdrawn.
- If a participant withdraws from the study, it should be confirmed if he/she still agrees for existing samples to be used in line with the original consent. If he/she withdraws consent for use of samples, destruction of any samples taken and not tested should be carried out in line with what was stated in the informed consent and local regulation. The Investigator must document the decision on use of existing samples in the site study records and inform the Global Study Team.

7.3 Lost to Follow-up

A participant will be considered lost to follow-up if he or she repeatedly fails to return for scheduled visits and is unable to be contacted by the study site.

The following actions must be taken if a participant fails to return to the clinic for a required study visit:

- The site must attempt to contact the participant and reschedule the missed visit as soon as possible and counsel the participant on the importance of maintaining the assigned visit schedule and ascertain whether the participant wishes to and/or should continue in the study.

- Before a participant is deemed lost to follow-up, the Investigator or designee must make every effort to regain contact with the participant (where possible, 3 telephone calls and, if necessary, a certified letter to the participant's last known mailing address or local equivalent methods). These contact attempts should be documented in the participant's medical record.
- Should the participant continue to be unreachable, he/she will be considered to have withdrawn from the study.
- Site personnel, or an independent third party, will attempt to collect the vital status of the participant within legal and ethical boundaries for all participants enrolled, including those who did not get investigational product. Public sources may be searched for vital status information. If vital status is determined as deceased, this will be documented and the participant will not be considered lost to follow-up. Sponsor personnel will not be involved in any attempts to collect vital status information.

Discontinuation of specific sites or of the study as a whole are handled as part of Appendix [A 9](#).

7.4 Stopping Rules, Progression to Next Study Part, and Termination of Study

7.4.1 Stopping Rules for an Individual Participant, at Any Time in the Study

Each participant in this study will receive a single dose of IMP. An individual participant will not receive IMP if any of the following occur in the participant in question:

- Withdraws consent after signing informed consent.
- Meets one or more of the exclusion criteria or fails to meet all inclusion criteria for study participation.

Each participant who has received IMP will be followed for the full study period unless consent is withdrawn specifically from further study participation, or the participant is lost to follow-up. Participants who have not received IMP, regardless of reason, will not be followed. Unless consent for follow-up is withdrawn, participants discontinued after receiving a partial dose of IMP will be followed for the full study period (up to and including Day 366, 52 weeks after IMP dosing) with all laboratory and clinical evaluations collected as defined in this CSP.

7.4.2 Stopping Rules for a Whole Cohort, Progression to Next Study Part, and Termination of Study

The Sponsor reserves the right to temporarily suspend or permanently terminate this study or a component of the study at any time.

Stopping rules as detailed below (general, cardiovascular, laboratory, and AZD7442 specific).

General Criteria

The study will be put on temporary hold (defined as stop of enrollment of participants into the study) pending further safety data analysis if any of the following criteria occur in participants receiving AZD7442:

- An SAE (including death) where there is a reasonable possibility that it is related to the IMP administration in any one participant.
- A severe non-serious adverse reaction where there is a reasonable possibility that it is related to the IMP administration in 2 or more participants in the same cohort, independent of, within, or not within the same system organ class.

The risk to all participants will be evaluated thoroughly prior to a decision as to whether to terminate the study prematurely or continue dosing in agreement with the regulatory authorities.

The DSMB will carefully review the totality of data, taking into account moderate non-serious AEs where there is a reasonable possibility that the AE is related to the IMP administration, the number of participants in which the AE occurs, and concurrency of more than one AE within the same participant.

Cardiovascular Criteria

- Two or more participants, that receive AZD7442, have QTc prolongation defined as QTcF > 500 ms, or a prolongation from baseline (pre-dose on Day 1) of > 60 ms, confirmed (persistent for at least 5 minutes) and determined post dose either during continuous 12 lead ECG monitoring or on a repeat 12 lead ECG.

Laboratory Findings

- One or more participants, who receive AZD7442, fulfill Hy's Law defined as "An increase in AST or ALT $\geq 3 \times$ ULN and TBL $\geq 2 \times$ ULN, where no other reason can be found to explain the combination of increases, eg, elevated serum ALP indicating cholestasis, viral hepatitis, another drug". The elevations do not have to be at the same time or within a specified time frame (see [Appendix D](#) for follow-up procedures).

Study Specific Stopping Criteria Related to AZD7442

- Anaphylactic reaction ([Appendix F](#)) considered related to the IMP in any participant.

- Any safety finding assessed as related to the IMP that, in the opinion of the Sponsor or the Investigator, warrants suspension of further dosing of participants until more fully assessed.

8 STUDY ASSESSMENTS AND PROCEDURES

- Study procedures and their timing are summarized in the SoA (Section [1.3](#)). Protocol waivers or exemptions are not allowed.
- Immediate safety concerns should be discussed with the Sponsor immediately upon occurrence or awareness.
- Adherence to the study design requirements, including those specified in the SoA, is essential and required for study conduct.
- All screening evaluations must be completed and reviewed to confirm that potential participants meet all eligibility criteria. The Investigator will maintain a screening log to record details of all participants screened and to confirm eligibility or record reasons for screening failure, as applicable.
- Procedures conducted as part of the participant's routine clinical management (eg, blood count) and obtained before signing of the ICF may be utilized for screening or baseline purposes provided the procedures met the protocol-specified criteria and were performed within the time frame defined in the SoA.
- A hierarchy of blood tests and wide visit windows are defined in Section [8.5.1](#) to provide flexible blood collection schedules. This will allow Investigators to determine the blood volume that can be safely drawn from each child based on the child's individual circumstances (eg, tests already conducted as part of the child's routine clinical management) without exceeding local recommendations. Repeat or unscheduled samples may be taken for safety reasons or for technical issues with the samples.

8.1 Efficacy Assessments

8.1.1 Monitoring COVID-19 Symptoms

Progression of COVID-19 will be captured and recorded in the eCRF.

To determine the incidence of infection in Cohort 1, when a participant develops at least one of the COVID-19 qualifying symptoms listed in [Table 13](#) after Day 1, the participant, his/her caretaker, or his/her legal representative must contact the study site. A sample will be collected for SARS-CoV-2 RT-PCR to confirm the participant is positive (see Section [8.6.1](#)). COVID-19 qualifying symptom(s), SARS-CoV-2 positive test results, and/or COVID-19 diagnosis will be collected and recorded in the eCRF as AEs.

In Cohorts 2 and 3, COVID-19 symptoms or signs listed in [Table 13](#) will only be recorded as

AEs when any of the following occur:

- The sign or symptom is serious according to the definition in Appendix B 2.
- The participant discontinues the study due to the sign or symptom.
- In the Investigator's judgment, the sign or symptom is not considered COVID-19 related.

Table 13 COVID-19 Qualifying Symptoms

Participant must present with at least one of the following symptoms:	
Duration	Symptom
No minimum duration	Fever
	Shortness of breath
	Difficulty breathing
Must be present for \geq 2 days	Chills
	Cough
	Fatigue
	Muscle aches
	Body aches
	Headache
	New loss of taste
	New loss of smell
	Sore throat
	Congestion
	Runny nose
	Nausea
	Vomiting
	Diarrhea
	Abdominal pain
	Poor appetite/feeding problems

CDC, Centers for Disease Control and Prevention; COVID-19, coronavirus disease 2019.

Adapted from [CDC 2020](#).

8.1.2 Severe COVID-19 Criteria

In all cohorts, severe COVID-19 will be characterized by a minimum of either pneumonia (fever, cough, tachypnea, or dyspnea, and lung infiltrates) or hypoxemia ($\text{SpO}_2 < 90\%$ in room air and/or severe respiratory distress) and a WHO Clinical Progression Scale score of 5 or higher ([Table 14](#)). Severe COVID-19 will be collected and recorded in the eCRF as an SAE.

Table 14 WHO Clinical Progression Scale

Patient state	Descriptor	Score
Uninfected	Uninfected, no viral RNA detected	0
Ambulatory mild disease	Asymptomatic; viral RNA detected	1
	Symptomatic; independent	2
	Symptomatic; assistance needed	3
Hospitalized: moderate disease	Hospitalized; no oxygen therapy ^a	4
	Hospitalized; oxygen by mask or nasal prongs	5
Hospitalized: Severe Disease	Hospitalized; oxygen by NIV or high flow	6
	Intubation and mechanical ventilation, $pO_2/FiO_2 \geq 150$ or $SpO_2/FiO_2 \geq 200$	7
	Mechanical ventilation $pO_2/FiO_2 < 150$ ($SpO_2/FiO_2 < 200$) or vasopressors	8
	Mechanical ventilation $pO_2/FiO_2 < 150$ and vasopressors, dialysis, or ECMO	9
Dead	Death	10

^a If hospitalized for isolation only, record status as for ambulatory patient.

ECMO, extracorporeal membrane oxygenation; FiO_2 , fraction of inspired oxygen; NIV, non-invasive ventilation; pO_2 , partial pressure of oxygen; SpO_2 , oxygen saturation, WHO, World Health Organization.
(Marshall et al 2020)

8.2 Safety Assessments

Planned time points for all safety assessments are provided in the SoA (Section 1.3).

8.2.1 Physical Examinations

A complete physical examination will be performed at screening followed by targeted physical examinations as specified in the SoA (Section 1.3).

- A complete physical examination will include, but not be limited to, assessment of height, weight, general appearance, head, ears, eyes, nose, throat, neck, skin, as well as cardiovascular, respiratory, abdominal, and nervous systems. Each clinically significant abnormal finding at screening will be recorded in the medical history.
- A targeted physical examination will include areas suggested by the medical history. Each clinically significant abnormal finding following IMP dosing will be recorded as an AE (Section 8.2).

All physical examinations will be performed by a licensed healthcare provider (eg, physician, physician assistant, or licensed nurse practitioner).

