5.1 Inclusion Criteria

Participants are eligible to be included in the study only if all the following criteria apply:

Age and Weight

- 1 Participant must be aged \geq 29 weeks GA to $<$ 18 years of age at the time of signing the informed consent (see Appendix A 3 for procedures around informed consent).
- 2 Participant must weigh a minimum of 1.5 kg.

Type of Participant and Disease Characteristics

COHORT 1: Participants who do not have COVID-19 and have not knowingly been exposed to a SARS-CoV-2 positive individual (pre-exposure prophylaxis):

- 3 At increased risk of severe COVID-19 for any of the following reasons:
 - (a) Immunocompromised state
 - (b) One or more comorbid conditions that increase the risk of severe COVID-19, eg, cardiovascular disease, including heart disease since birth, malignancy, chronic kidney disease, and genetic, neurologic, or metabolic conditions.
- 4 Medically stable defined as disease not requiring significant change in therapy or hospitalization for worsening disease during the one month prior to enrollment, with no acute change in condition at the time of study enrollment as judged by the Investigator.
- 5 Documented negative SARS-CoV-2 RT-PCR test collected \leq 3 days prior to Day 1 or a negative rapid SARS-CoV-2 antigen test at screening.
- 6 Prior to enrollment, participants must not have had COVID-19 symptoms (Table 13) within 10 days of dosing.

7 Increased risk for SARS-CoV-2 infection, defined as those whose locations or circumstances put them at appreciable risk of exposure to SARS-CoV-2 and COVID-19, based on available risk assessment at time of enrollment.

COHORT 2: Participants with COVID-19 and mild to moderate symptoms (treatment):

8 At increased risk of severe COVID-19 for any of the following reasons:

- (a) Immunocompromised state
- (b) One or more comorbid conditions that increase the risk of severe COVID-19 (see list in 3[b])

9 Medically stable defined as disease not requiring significant change in therapy or hospitalization for worsening disease during the one month prior to enrollment, with no acute change in condition at the time of study enrollment as judged by the Investigator.

10 Documented positive SARS-CoV-2 RT-PCR test collected \leq 3 days prior to Day 1 or a positive rapid SARS-CoV-2 antigen test at screening.

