8.3.7 Adverse Events Based on Examinations and Tests

The results from the CSP mandated laboratory tests and vital signs will be summarized in the CSR.

Deterioration as compared to baseline in protocol-mandated safety assessments should therefore only be reported as AEs if they fulfill any of the SAE criteria, are the reason for discontinuation of treatment with the investigational product or are considered to be clinically relevant as judged by the Investigator (which may include, but are not limited to, consideration as to whether treatment or non-planned visits were required or other action was taken with the study intervention, eg, dose adjustment or drug interruption).

If deterioration in a laboratory value/vital sign is associated with clinical signs and symptoms, the sign or symptom will be reported as an AE and the associated laboratory result/vital sign will be considered as additional information. Wherever possible the reporting Investigator uses the clinical, rather than the laboratory term (eg, anemia versus low hemoglobin value). In the absence of clinical signs or symptoms, clinically relevant deteriorations in non-mandated parameters should be reported as AE(s).

Any new or aggravated clinically relevant abnormal medical finding at a physical examination as compared with the baseline assessment will be reported as an AE unless unequivocally related to the disease under study.

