#### 4.2.2.1 Adverse Events

Adverse Events will be collected throughout the study from date of informed consent until the end of the follow-up. The MedDRA will be used to code the AEs using the latest available version.

Treatment-emergent AEs are those AEs with onset date/time at or after dosing.

A listing will cover details for each individual AE including MedDRA SOC, PT, reported term, seriousness, start and stop date/time, relatedness to IMP, intensity (mild, moderate, severe and CTCAE grade 1-5), actions taken, time from last dose, whether or not leading to withdrawal from the study, AESI identification and outcome.

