#### 4.2.2.4 Physical Examination

A Complete Physical Examination will include, but not be limited to, assessment of height, weight, general appearance, head, ears, eyes, nose, throat, neck, skin, as well as cardiovascular, respiratory, abdominal, and nervous systems.

Abnormal baseline/results of the Physical Examination will be documented in medical history.

Any new or aggravated clinically relevant abnormal medical physical examination finding compared to the baseline assessment will be reported as an AE.

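### Protocol 8.2.1 records post-dose examination findings as AEs without comparison to baseline, contradicting Protocol 8.3.7 and SAP 4.2.2.4; a stable pre-existing finding could be counted as a TEAE

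*Protocol*

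**What the plan says.** Three places give a rule for examination findings.

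- **Protocol 8.2.1** sorts findings by when they are seen. At screening: "Each clinically significant abnormal finding at screening will be recorded in the medical history". After dosing: "Each clinically significant abnormal finding following IMP dosing will be recorded as an AE". It then refers the reader to Section 8.2, which only points to the schedule of activities and holds no AE rule. The section also sets the scope of the post-dose examination: "A targeted physical examination will include areas suggested by the medical history".
- **Protocol 8.3.7** compares with baseline: "Any new or aggravated clinically relevant abnormal medical finding at a physical examination as compared with the baseline assessment will be reported as an AE", with the exemption "unless unequivocally related to the disease under study".
- **SAP 4.2.2.4** also compares with baseline but has no exemption: "Any new or aggravated clinically relevant abnormal medical physical examination finding compared to the baseline assessment will be reported as an AE".

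The SAP classifies by date alone (4.2.2.1): "Treatment-emergent AEs are those AEs with onset date/time at or after dosing". SAP 3.3.5 sets a completely unknown AE start date to the date and time of dosing, unless the event is known to have ended before dosing.

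Protocol Appendix B 1 defines an AE as something that develops, and includes the worsening of a condition already present.

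**The concern.** The rules give different answers for the same child. Take a clinically significant sign noted at screening and found unchanged at a later visit. Under 8.3.7 and SAP 4.2.2.4 it is not an AE. Under the literal words of 8.2.1 it is.

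The case is a natural one in this trial. The post-dose examination is directed at areas with known history and is scheduled at Visits 2 to 6. Eligibility for Cohorts 1 and 2 (Protocol 5.1) requires a risk condition: "At increased risk of severe COVID-19 for any of the following reasons". The examples there include heart disease since birth and neurologic conditions. SAP section 2 says that Cohort 3 has no participants, so this selection applies to everyone analysed.

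At stake is TEAE incidence. It belongs to the co-primary safety objective, is reported with exact confidence intervals, and has no control arm to show the background rate. About 33 sites were planned, and they could follow different written rules.

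**Working it through.** **1. The three rules side by side**

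| | Protocol 8.2.1 | Protocol 8.3.7 | SAP 4.2.2.4 |
|---|---|---|---|
| Compared with baseline? | No | Yes, new or aggravated | Yes, new or aggravated |
| Disease-under-study exemption? | No | Yes | No |
| Points to the AE rule for examinations? | No, cites Section 8.2 | Is that rule | Not applicable |

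The next section, 8.2.2 on vital signs, does cite 8.3.7. The reference in 8.2.1 therefore looks like a drafting slip.

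**2. From an AE entry to a TEAE**

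If a site enters a stable finding as an AE, three outcomes follow from SAP 3.3.5 and 4.2.2.1:

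- Onset entered as the true pre-dose date: not a TEAE. It could still be counted in the overview of participants with any AE.
- Onset entered as the visit date, or any date at or after dosing: a TEAE.
- Start date completely unknown: imputed to dosing, so a TEAE unless the event ended before dosing. A stable finding has not ended.

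The SAP describes no step that removes such an entry.

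**3. Size**

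The plan gives no figure to reproduce. The only input from the documents is n = 46, the full analysis set in SAP section 2. The Safety Analysis Set, to which SAP Table 2 assigns these endpoints, is likewise everyone who received the product.

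- Weight of one child: 1/46 = 2.2 percentage points. SAP 4.2.2.1 presents incidence by cohort and route, where denominators are smaller and each child weighs more.
- Illustration with the SAP's own exact Clopper-Pearson 95% intervals. The starting count and the number of added children are assumptions:

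| Children with a TEAE | Incidence | 95% CI |
|---|---|---|
| 23/46 (assumed start) | 50.0% | 34.9 to 65.1 |
| 28/46 (5 added) | 60.9% | 45.4 to 74.9 |
| 33/46 (10 added) | 71.7% | 56.5 to 84.0 |

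**4. A ceiling**

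Let b be TEAE incidence under the 8.3.7 rule, q the share of children with a stable clinically significant finding, and r the share of those recorded as AEs with a post-dose onset. If q is independent of b, the inflation is (1 − b) × q × r. All three are assumed, with b = 0.5 and q = 0.2 to 0.6:

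- r = 1: 0.5 × 0.2 = 10 points to 0.5 × 0.6 = 30 points.
- r = 0.25: 2.5 to 7.5 points.
- r = 0: none.

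The 10 to 30 points need every site to follow 8.2.1 literally and to date every such finding after dosing.

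**The case against.** The strongest reply is that the AE definition already settles the matter. Protocol 8.3 refers to Appendix B for what an AE is and makes investigators responsible for recording events that meet that definition. An unchanged murmur neither develops nor deteriorates. Read as a whole, 8.2.1 may also mean only that findings known at screening go to medical history and findings arising later become AEs. This stands as mitigation: many investigators will do the right thing. It does not remove an instruction that covers each post-dose finding, placed in the section that examiners use.

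A reader might also draw three stronger conclusions that the documents do not support.

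- *Every stable finding becomes a TEAE at the first post-dose examination.* It does not, because the onset date decides. Start date is a collected variable (Protocol 8.3.2), and a finding in the screening history should have a pre-dose onset.
- *The same finding is counted again at each visit.* AEs carry start and stop dates, so a persisting finding is one ongoing event. Nothing calls for a new entry at each visit.
- *Inflation could not be told apart from a drug effect.* Without controls the incidence itself cannot be corrected by comparison. But causality is recorded for each AE, the overview presents relationship to the product, and medical history and AEs are both listed with preferred terms and dates. Carried-over conditions can therefore be traced.

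**Conclusion.** The contradiction is real and lies in the text: 8.2.1 conflicts with 8.3.7 and SAP 4.2.2.4, and the exemption in 8.3.7 has no counterpart in the SAP. The consequence is possible, not certain. It requires a site to apply 8.2.1 literally and then either to date the onset at or after dosing or to leave the start date completely unknown.

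The size cannot be determined from the documents. What can be said is that one such child moves overall TEAE incidence by 2.2 points at n = 46. A range of 10 to 30 points should be read only as a ceiling under the assumed b and q with complete misrecording. The listed risk conditions, such as immunocompromise or chronic kidney disease, need not produce an examination sign at all.

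The point is of modest weight. Sample size, power and alpha are untouched, but it concerns a co-primary safety measure and is cheap to put right.

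**What to change.** 1. **Protocol 8.2.1:** adopt the 8.3.7 rule, so that a post-dose finding is an AE only if it is new or aggravated against baseline, subject to the same disease-under-study exemption. Change the cross-reference from Section 8.2 to Section 8.3.7.
2. **SAP 4.2.2.4:** state whether the exemption applies, and to which cohorts. Protocol 8.1.1 records COVID-19 symptoms as AEs in Cohort 1 but restricts this in Cohorts 2 and 3, so the answer should agree with that section.
3. **Before database lock:** query each examination-based AE whose term matches an unchanged medical-history entry. Do not count confirmed stable findings as TEAEs, and document how many were reclassified.

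Enrolment has stopped, so rewording 8.2.1 cannot change entries already made and helps only examinations still to come. The third step is the one that protects the data in hand, and it fits the pre-lock review already planned in SAP 4.1.1.1. The cost is one sentence and one reference in the protocol, one sentence in the SAP, and one extra data-review query. Visits, samples and sample size do not change.
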